2.1.2 Prior or concomitant medications

All medications taken within 30 days before screening and until the end of the study, including oral corticosteroids and asthma controller medications are to be reported in the case report form pages.

All medications will be coded using the World Health Organization-Drug Dictionary (WHO-DD) using the version currently in effect at Sanofi at the time of database lock.

• Prior medications are those the patient used prior to first IMP intake. Prior medications can be discontinued before first administration or can be ongoing during treatment phase.

Concomitant medications are any treatments received by the patient concomitantly to the IMP, from the first administration of IMP to the last administration of IMP + 98 days (2 weeks after last administration of IMP plus 12 weeks of residual treatment epoch) or till rollover to the LTS12551 study. A given medication can be classified both as a prior medication and as a concomitant medication. Concomitant medications do not include medications started during the posttreatment epoch (as defined in the observation period in Section 2.1.4).

• Posttreatment medications are those the patient took in the period running from the last administration of IMP + 99 days up to the end of the study.

Oral corticosteroids

To be enrolled in the study, a patient should be on well-documented, regular prescribed treatment of maintenance systemic corticosteroids in the 6 months prior to Visit 1 and using a stable OCS (ie, no change of OCS dose) dose for 4 weeks prior to Visit 1. At Visit 1, patients currently using other forms of maintenance OCS will have their corticosteroids switched to

Statistical Analysis Plan SAR231893-EFC13691 - dupilumab 18-May-2017 Version number: 1

prednisone/prednisolone at a dose clinically equivalent to their current stable OCS maintenance dose. During the course of the study, including the post-treatment period, patients will receive variable doses of OCS.

Inhaled corticosteroid with a second or third controller

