2.1.4 Safety endpoints

The safety analysis will be based on the reported adverse events (AE) and other safety information, such as clinical laboratory data, vital signs, physical examination, electrocardiogram (ECG), etc.

Observation period

The observation period will be divided into 4 epochs:

- The **screening** epoch is defined as the time from the signed informed consent date up to the first administration of the IMP.
- The **treatment** epoch is defined as the time from the first administration of the IMP to the last administration of the IMP + 14 days or until the patient enters the extension study.
- The **residual treatment** epoch is defined as the time from the last administration of the IMP + 15 days to the last administration of the IMP + 98 days or until the patient enters the extension study.

The treatment-emergent adverse event (TEAE) period will include both **treatment** and **residual treatment** epochs.

• The **posttreatment** epoch is defined as the period of time starting the day after the end of the treatment-emergent adverse event period up to the end of the study (defined as last protocol-planned visit or lost to follow-up or the resolution/stabilization of all serious adverse events and adverse events with prespecified monitoring).

The on-study observation period is defined as the time from start of treatment until the end of the study.

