2.4.2 Prior or concomitant medications

The prior and concomitant medications will be presented for the randomized population.

Medications will be summarized by treatment group according to the WHO-DD dictionary, considering the first digit of the Anatomical Therapeutic Chemical (ATC) class (anatomic category) and the first 3 digits of the ATC class (therapeutic category). All ATC codes corresponding to a medication will be summarized, and patients will be counted once in each ATC category (anatomic or therapeutic) linked to the medication. Therefore patients may be counted several times for the same medication.

The table for prior medications will be sorted by decreasing frequency of ATC followed by all other therapeutic classes based on the overall incidence across treatment groups. In case of equal frequency regarding ATCs (anatomic or therapeutic categories), alphabetical order will be used.

The tables for concomitant medications will be sorted by decreasing frequency of ATC followed by all other therapeutic classes based on the incidence in the dupilumab group. In case of equal frequency regarding ATCs (anatomic or therapeutic categories), alphabetical order will be used.

Concomitant medications will be summarized for the treatment epoch and treatment emergent period separately.

Inhaled corticosteroid in combination with other controllers will be summarized separately.

Oral corticosteroids

Compliance to OCS

Compliance to the prescribed OCS dose will be calculated from Visit 3 (Week 0) until Visit 11 (Week 24) for patients who stay in the study until that time, or until the later between end of treatment and the last scheduled visit that occurred where the OCS dose adjustment is still recorded for patients who withdraw from the study before Visit 11. For each day, a patient is considered as compliant to the prescribed OCS if the patient takes the dose as prescribed. Days with missing OCS dose use record will be considered as non-compliant. Days when the ediary record of prescribed OCS dose was later corrected by the investigator (which will result in an inconsistency between the answer to the compliance question in ediary and compliance derived from comparing the actual dose to the prescribed dose) will be excluded from the compliance calculation.

Percentage of OCS compliance for a patient will be defined as the number of days that the patient was compliant divided by the total number of days during the period defined above.

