2.4.3.1 Extent of investigational medicinal product exposure

The extent of IMP exposure will be assessed by the duration of IMP exposure.

Duration of IMP exposure is defined as last dose date – first dose date + 14 day, regardless of unplanned intermittent discontinuations (see Section 2.5.3 for calculation in case of missing or incomplete data). Duration of IMP exposure will be summarized descriptively as a quantitative variable (number, mean, SD, median, minimum, and maximum). In addition, duration of treatment exposure will also be summarized categorically by numbers and percentages for each of the following categories and cumulatively according to these categories:

- >0 and ≤ 2 weeks
- >2 and \leq 4 weeks
- >4 and ≤ 6 weeks
- >6 and \leq 8 weeks

- >8 and ≤ 12 weeks
- >12 and ≤ 16 weeks
- >16 and ≤ 20 weeks
- >20 and \leq 24 weeks
- >24 Weeks
- Additionally, the cumulative duration of treatment exposure will be provided, defined as the sum of the duration of treatment exposure for all patients, and will be expressed in patient years.

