- All treatment-emergent adverse events leading to permanent treatment discontinuation or drug interruption, by primary SOC, HLGT, HLT, and PT, showing the number (%) of patients sorted by the internationally agreed SOC order. The other levels (HLGT, HLT, PT) will be presented in alphabetical order
- All treatment-emergent adverse events leading to permanent treatment discontinuation or drug interruption, by primary SOC and PT, showing the number (%) of patients sorted by the internationally agreed SOC order and by decreasing incidence of PTs within each SOC

Analysis of all treatment-emergent adverse event(s) of special interests and other selected AE groupings

- All treatment-emergent adverse events, by selected standardized MedDRA query (SMQ) and PT or by laboratory values (as in ALT elevation), showing the number (%) of patients with at least 1 PT, sorted by decreasing incidence of PTs within each SMQ
- For each prespecified AESI and selected events,
 - Number (%) of patients with any of the specific TEAE
 - Number (%) of patients with any of the specific serious AE (regardless of treatment emergent status)

- Number (%) of patients with any of the specific treatment emergent serious AE
- Number (%) of patients with any of the specific AE leading to death
- Number (%) of patients with any of the specific TEAE leading to permanent study drug discontinuation
- Number (%) of patients with any of the specific TEAE by maximum intensity, corrective treatment, and final outcome
- Number of the specific TEAE adjusted by exposure duration
- All of the specific TEAE, by PT, showing the number (%) of patients, sorted by decreasing incidence of PT
- K-M estimates of cumulative incidence of the specific TEAE at Weeks 12 and 24 and K-M plot may be provided to depict the course of onset over time if the number of events is large enough
- Number (%) of patients with injection site reactions by the related injection
- Number (%) of patients with different number of injection site reactions

Analysis of pretreatment adverse events

- All pretreatment adverse events by primary SOC and PT, showing the number (%) of patients with at least 1 pretreatment adverse event, sorted by the internationally agreed SOC order and decreasing incidence of PTs within each SOC

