2.5.3 Missing data

For categorical variables, patients with missing data are not included in calculations of percentages unless otherwise specified. When relevant, the number of patients with missing data is presented.

Handling of missing answer to the 7^{th} question in ACQ-7

If the score is missing from the site report, the FEV1 % predicted value from spirometry test will be used to derive the 7th score. Only the spirometry performed on the same day when ACQ-7 is evaluated will be used. And if there are multiple FEV1% predicted values available on the same day, the lowest one will be used to score the 7^{th} item. If the score of the 7^{th} question is still missing but the questionnaire is complete at the prior visit, the missing score for the 7th question

will be imputed as: (score of the 7th question at the prior visit) \times (sum of scores of the first six questions at the current visit) / (sum of scores of the first six questions at the prior visit). If the questionnaire from the prior visit is not complete either or if the ACQ-7 score at the prior visit is 0, which makes it infeasible to implement the algorithm, the missing score will be imputed as the average of the other six questions at the current visit. If scores of the first six questions are missing, then the ACQ-7 score for the current visit will be missing.

Handling of computation of treatment duration if investigational medicinal product end of treatment date is missing

For the calculation of the treatment duration, the date of the last dose of IMP is equal to the date of last administration reported on the Investigational Product Administration report form page. If this date is missing, the exposure duration should be left as missing.

The last dose intake should be clearly identified in the case report form and should not be approximated by the last returned package date.

Handling of medication missing/partial dates

No imputation of medication start/end dates or times will be performed. If a medication date or time is missing or partially missing and it cannot be determined whether it was taken prior or concomitantly, it will be considered as a prior and a concomitant medication.

Handling of adverse events with missing or partial date/time of onset

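### The exposure-adjusted AESI counts pair events counted to 98 days after the last dose with the SAP's only exposure duration, which ends at 14 days; patients who do not roll over carry up to 84 unmatched days

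*SAP*

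**What the plan says.** SAP 2.4.5.1, in the list of summaries for each prespecified AESI and selected event, includes the "Number of the specific TEAE adjusted by exposure duration". It gives no formula, unit or cross-reference.

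The event window comes from SAP 2.1.4: "The treatment-emergent adverse event (TEAE) period will include both" the treatment epoch and the residual treatment epoch. The residual epoch runs "from the last administration of the IMP + 15 days to the last administration of the IMP + 98 days", or stops at entry to the extension study if that comes first. Protocol 11.3.2 describes the same period.

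The duration comes from SAP 2.4.3.1: "Duration of IMP exposure is defined as last dose date – first dose date + 14 day". That section also sums it over patients and expresses it in patient-years. SAP 2.5.3 uses the term in the same sense. On a missing last-dose date it says: "If this date is missing, the exposure duration should be left as missing". The SAP defines no time at risk for the treatment-emergent period.

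**The concern.** A rate needs its events and its person-time to come from the same window. Here the numerator can include events from the 12 weeks after the denominator has stopped accruing. The gap also depends on what happens to the patient. Someone who completes treatment and enters the extension study has almost none. Someone who completes and stays for the post-treatment period, or who stops early and so cannot roll over, can have the full gap.

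The groupings include hypersensitivity, severe or serious infections and hepatic disorders, and safety is a stated secondary objective. A reader would take the adjusted counts as events per unit of time observed. They would instead depend partly on how many patients in each arm rolled over.

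**Working it through.** **Inputs**
- Treatment-emergent window: to last dose + 98 days or extension entry (SAP 2.1.4).
- Exposure: last dose − first dose + 14 days (SAP 2.4.3.1).
- Last scheduled dose for a completer: Week 22, which is 154 days after the first. The Week 24 visit lists no IMP administration (Protocol 10.1.2.4 and 10.1.2.4.1).
- Rollover: open to patients who complete 24 weeks and attend the end-of-treatment visit (Protocol 8.2.6). They skip the post-treatment period (SAP 1.4).
- Database lock: about 30 days after the last patient's Week 24 visit, with later data in an addendum (SAP 4).

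**The plan's own figure.** SAP 2.1.2 describes the 98 days as "2 weeks after last administration of IMP plus 12 weeks of residual treatment epoch". Check: 14 + 12 × 7 = 98. It reproduces. The unmatched stretch is 98 − 14 = 84 days.

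**Per-patient windows.** With d = last dose day − first dose day, the exposure is d + 14 and the full event window is d + 98.

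| Patient | Exposure (days) | Event window (days) | Ratio |
|---|---|---|---|
| Completer, rolls over at Week 24 | 154 + 14 = 168 | 168 | 1.00 |
| Completer, enters extension 14 days later | 168 | 182 | 1.08 |
| Completer, no rollover, full follow-up | 168 | 154 + 98 = 252 | 1.50 |
| Last completer, no rollover, cut at lock | 168 | 168 + 30 = 198 | 1.18 |
| Stops after Week 4 dose | 28 + 14 = 42 | 28 + 98 = 126 | 3.00 |
| Day 1 dose only | 14 | 98 | 7.00 |

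**From window ratio to rate inflation.** Let h be the event rate in the residual epoch divided by the rate in the treatment epoch. The documents give no value, so h is an assumption. For a non-rollover completer with full follow-up, inflation = 1 + (84/168) × h = 1 + 0.5h:
- h = 0 gives 1.00
- h = 0.5 gives 1.25
- h = 1 gives 1.50
- h = 1.5 gives 1.75

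**Arm level.** Take completers only, with h = 1, full follow-up and a share r rolling over. Inflation is then 1.5 − 0.5r. The documents do not give r, so a range is shown:
- r = 0% gives 1.50
- r = 50% gives 1.25
- r = 80% gives 1.10
- r = 90% gives 1.05

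If r were 90% in one arm and 80% in the other, the spurious rate ratio would be 1.05/1.10 = 0.95. At 90% and 70% it would be 1.05/1.15 = 0.91. With equal shares and equal h it is 1.00.

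**Early stoppers in a summed denominator.** One Day-1-only patient among 89 rollover completers gives (98 + 89 × 168)/(14 + 89 × 168) = 15050/14966 = 1.006.

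**After the fix.** With time at risk as the denominator, a non-rollover completer gives 252/252 = 1.00. With events restricted to last dose + 14 days, it is 168/168 = 1.00.

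**The case against.** The strongest reply is that the AESI line never says it uses the 2.4.3.1 duration. That is true, so the denominator is an inference. But a programmer following the SAP has no other defined exposure duration to use, and the term has that meaning elsewhere in the document. If something else was intended, the text has to say so.

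Several limits on size stand:
- The figure 1.5 compares days. It becomes a rate inflation only if events are as frequent after treatment as during it and follow-up is complete. Injection site reactions and symptomatic IMP overdose are tied to dosing and would barely move.
- Database lock shortens the window for late completers.
- A patient who leaves the study soon after the last dose has little or no mismatch.
- SAP 2.4.5 describes the safety analysis as essentially descriptive, so no decision rule rests on this line.
- Kaplan-Meier cumulative incidence handles unequal follow-up by censoring. However, SAP 2.4.5.1 makes it optional, depending on event numbers.

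A reader might also infer that early stoppers distort the result three- or seven-fold. Those are per-patient ratios. In a summed denominator each such patient adds at most 84 unmatched days, as the 1.006 example shows.

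A further tempting step is to call the crude percentages wrong and ask for treatment-epoch tables, since SAP 2.4.2 says "Concomitant medications will be summarized for the treatment epoch and treatment emergent period separately". The crude tables use the safety population as denominator and have no such mismatch. Their unequal follow-up is a separate matter, and the handling of medications places no requirement on adverse events.

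**Conclusion.** The mismatch is real on the only definition the SAP supplies. It is confined to the exposure-adjusted AESI and selected-event counts. The event window exceeds the denominator by up to 84 days for a patient who does not roll over and by about 0 days for one who rolls over at Week 24. For a non-rollover completer the inflation is up to 1.5-fold, given a constant event rate and full follow-up. For a last completer cut at lock, the same constant-rate assumption gives 1.18.

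The documents do not support a general statement that AESI rates are inflated 1.5-fold. The arm-level figure depends on the non-rollover share, which is not given.

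Nor do they establish a biased comparison between arms. That needs rollover or discontinuation to differ by arm. Protocol 4.2.2 reports more discontinuation on placebo than on dupilumab in earlier trials. If that recurred, it would tend to inflate the placebo rates more. But it also reports low discontinuation on dupilumab, and nothing is quantified for this trial.

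The line should be corrected because following it as written gives a mismatched rate and the remedy is cheap.

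**What to change.** In SAP 2.4.5.1, define the denominator as time at risk in the treatment-emergent period: from first dose to the earliest of last dose + 98 days, extension entry, last contact or database lock. State the unit, for example events per patient-year.

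Alternatively, keep the 2.4.3.1 duration and count only events up to last dose + 14 days. Either choice matches the windows. The first keeps all treatment-emergent events; the second gives an on-treatment rate.

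The cost is one sentence in the SAP and a slightly different derivation for one descriptive summary. No new data are needed. Separate tables for the treatment epoch are optional.

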2.4.5.2 Deaths

The following summaries of deaths will be generated for the safety population.

• Number (%) of patients who died by study period (on-study, on-treatment, post-study) Treatment-emergent adverse events leading to death (death as an outcome on the adverse event case report form page as reported by the Investigator) by primary SOC, HLGT, HLT, and PT showing number (%) of patients sorted by internationally agreed SOC order, with HLGT, HLT, and PT presented in alphabetical order within each SOC.

- All pretreatment adverse events leading to death by primary SOC and PT, showing the number (%) of patients, sorted by the internationally agreed SOC order and decreasing incidence of PTs within each SOC
- Deaths in nonrandomized patients or in randomized but not treated patients will be summarized separately.

2.4.5.3 Analyses of laboratory variables

The summary statistics (including number, mean, median, Q1, Q3, standard deviation, minimum and maximum) of all laboratory variables (central laboratory values and changes from baseline) will be calculated for each visit or study assessment (baseline, each post baseline time point, last on-treatment and/or worst on-treatment value) by treatment group. For each continuous laboratory variables listed in Section 2.1.4.3, mean changes from baseline with the corresponding standard error will be plotted over time (at same time points) in each treatment group. This section will be organized by biological function as specified in Section 2.1.4.3.

The incidence of PCSAs (list provided in Appendix J) at any time during the treatment-emergent adverse event period will be summarized by biological function and treatment group whatever the baseline level and/or according to the following baseline status categories:

- Normal/missing
- Abnormal according to PCSA criterion or criteria

For parameters for which no PCSA criteria are defined, similar table(s) using the normal range will be provided.

For PCSA analyses, the laboratory measurements obtained at either scheduled or unscheduled visits should be used; and, both the centralized and local test results should be used, as long as their available dates/time is different from each other's. Centralized data will be used preferentially to the local measures in the PCSA analyses when measurements are performed on the same date and at the same time for a given laboratory test.

Drug-induced liver injury

If there is imbalance in the incidence of liver-related adverse events across the treatment groups, the following analysis of liver-related adverse events will be performed.

The liver function tests, namely AST, ALT, alkaline phosphatase, and total bilirubin, are used to assess possible drug-induced liver toxicity. The proportion of patients with PCSA values at any postbaseline visit by baseline status will be displayed by treatment group for each parameter. The proportion of patients with PCSA values at any postbaseline visit will also be displayed by duration of exposure for each treatment group.

Time to onset of the initial ALT and AST elevation (>3 x ULN) and total bilirubin elevation (>2 x ULN) (time to first observation of ALT > 3 x ULN or total bilirubin > 2 x ULN, whichever comes first) will be analyzed using Kaplan-Meier estimates, presented by treatment group.

Statistical Analysis Plan SAR231893-EFC13691 - dupilumab 18-May-2017 Version number: 1

Consideration should be given to the impact of the spacing of scheduled tests. A graph of distribution of peak values of ALT versus peak values of total bilirubin will also be presented. Note that the ALT and total bilirubin values are presented on a logarithmic scale. The graph will be divided into 4 quadrants with a vertical line corresponding to 3 x ULN for ALT and a horizontal line corresponding to 2 x ULN for total bilirubin.

Listing of possible Hy's law cases identified by treatment group (eg, patients with any elevated ALT>3 x ULN, and associated with an increase in bilirubin $\ge 2 \times ULN$) with ALT, AST, alkaline phosphatase, total bilirubin, and the following complementary parameters: conjugated bilirubin, creatine phosphokinase, serum creatinine, HCV RNA.

Summarize the normalization by parameter (to $\leq 1 \times ULN$ or return to baseline) of elevated liver function tests by categories of elevation (3 x, 5 x, 10 x, 20 x ULN for ALT and AST, 1.5 x ULN for alkaline phosphatase, and 1.5 x and 2 x ULN for total bilirubin), with the following categories of normalization: never normalized, normalized despite treatment continuation of IMP, or normalized after IMP discontinuation. Note that a patient will be counted only under the maximum elevation category.

Change in Blood Eosinophil

Mean changes from baseline in eosinophil with the corresponding standard error will be plotted over time in each treatment group for patients with baseline blood eosinophil < 0.5 Giga/L and patients with baseline blood eosinophil ≥ 0.5 Giga/L. Number (%) of patients with post-baseline peak blood eosinophil ≥ 1 Giga/L, ≥ 3 Giga/L and ≥ 5 Giga/L will also be summarized in each treatment group and by baseline blood eosinophil status (All, < 0.5 Giga/L).

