10.4.3 General guidelines for reporting adverse events

- All AEs, regardless of seriousness or relationship to IMP/NIMP, spanning from the signature of the informed consent form until the end of the study as defined by the protocol for that patient, are to be recorded on the corresponding page(s) or screen(s) of the e-CRF.
- Protocol defined asthma exacerbation events are collected as efficacy endpoints via the asthma exacerbation form. These events should not be reported as AEs unless they fulfill a seriousness criterion.
- Whenever possible, diagnosis or single syndrome should be reported instead of symptoms. The Investigator should specify the date of onset, intensity, action taken with respect to IMP, corrective treatment/therapy given, additional investigations performed, outcome, and his/her opinion as to whether there is a reasonable possibility that the AE was caused by the IMP or by the study procedure(s). In studies that require the use of combined/multiple IMPs/NIMPs, the GSO with input from other appropriate study team members must determine if the causal relationship will either be assessed for the combined product as a regimen or as distinct entities. The GSO must communicate this decision to the study team for inclusion in the protocol and AE CRF.
- The Investigator should take appropriate measures to follow all AEs until clinical recovery is complete and laboratory results have returned to normal, or until progression has been stabilized, or until death, in order to ensure the safety of the patients. This may imply that observations will continue beyond the last planned visit per protocol, and that additional investigations may be requested by the monitoring team up to as noticed by the Sponsor. Patients who experience an ongoing SAE or an AESI, at the prespecified study end-date, should be followed until resolution, stabilization, or death and related data will be collected. The duration of poststudy follow-up and reporting of AEs will be specified (eg, until recovery).

- When treatment is prematurely discontinued, the patient's observations will continue until the end of the study as defined by the protocol for that patient.
- Laboratory, vital signs or ECG abnormalities are to be recorded as AEs only if:
 - Symptomatic and/or
 - Requiring either corrective treatment or consultation, and/or
 - Leading to IMP discontinuation or modification of dosing, and/or
 - Fulfilling a seriousness criterion, and/or
 - Defined as an AESI

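### The Hy's law listing and ALT-bilirubin graph appear only if liver adverse events are imbalanced between arms, an undefined trigger unsuited to outputs where one patient matters

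*SAP*

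**What the plan says.** SAP 2.4.5.3 first sets out laboratory summaries that carry no condition: descriptive statistics by visit, worst on-treatment values, and the incidence of potentially clinically significant abnormalities (PCSAs) by treatment group. The liver injury subsection then begins with a condition: "If there is imbalance in the incidence of liver-related adverse events across the treatment groups". Under that sentence come the liver PCSA tables by baseline status and exposure, time to first ALT or bilirubin elevation, the normalization summary, and two patient-level outputs: "A graph of distribution of peak values of ALT versus peak values of total bilirubin will also be presented", and "Listing of possible Hy's law cases identified by treatment group". The listing is defined by ALT >3 x ULN with bilirubin ≥2 x ULN.

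The SAP does not say how large a difference counts as an imbalance. It does not say which events are liver-related either. Table 5 (SAP 2.1.4.1) contains a hepatic SMQ grouping, but the condition does not refer to it.

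Protocol 10.4.3 decides which laboratory findings enter the adverse event data: "Laboratory, vital signs or ECG abnormalities are to be recorded as AEs only if" at least one of five conditions is met. Being symptomatic is one and needing treatment or a consultation is another. The rest are "Leading to IMP discontinuation or modification of dosing, and/or", "Fulfilling a seriousness criterion, and/or" and "Defined as an AESI".

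**The concern.** A Hy's law listing and an ALT-bilirubin graph exist to find individual patients. One such patient is worth seeing whether or not the arms differ. A between-arm difference in adverse event counts is therefore the wrong kind of condition for them, and with no threshold the decision is left open until the unblinded counts are known.

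The condition also runs in the wrong direction. Both outputs come from laboratory values and could pick up cases that a site did not recognise or report. Making them depend on reported adverse events removes that check.

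At stake is whether the study report contains a display that puts ALT and bilirubin side by side for the same patient. Efficacy results are unaffected.

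**Working it through.** There is no figure in the plan to reproduce. The check sets the condition against the protocol's recording rules and then illustrates what an undefined imbalance could mean.

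**Step 1. Which asymptomatic laboratory findings can reach the trigger?** Inputs: Protocol 10.3.3 (withdrawal criteria), 10.4.1.2 (serious events), 10.4.1.3 (events of special interest) and 10.4.3 (recording rule).

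| Asymptomatic finding | Adverse event? | Route |
|---|---|---|
| ALT >3 x ULN with bilirubin >2 x ULN | Yes | Listed as medically important (10.4.1.2); withdrawal criterion (10.3.3) |
| ALT >10 x ULN | Yes | Listed as medically important (10.4.1.2) |
| ALT >5 x ULN, or >8 x ULN if baseline >2 x ULN | Yes | Event of special interest (10.4.1.3) |
| Isolated ALT >3 to 5 x ULN (up to 8 x ULN if baseline >2 x ULN), or bilirubin >2 x ULN alone; no treatment, consultation or dosing change | Need not be | No condition in 10.4.3 met |

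Only the last row is invisible to the trigger. Those patients would be points on the graph, but they are not Hy's law cases. Two small edges remain. The listing uses bilirubin ≥2 x ULN, whereas the serious-event and withdrawal rules use >2 x ULN. The listing also does not say whether the two rises must coincide, so rises at different times might qualify without having met the serious-event definition.

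**Step 2. How many recorded cases could fail to count as an imbalance?** Inputs: n = 90 per arm (SAP 1.3, randomized numbers; the safety population may differ slightly). Assumption: imbalance means two-sided Fisher p < 0.05. For k patients in one arm and none in the other, with equal arms,

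p = 2 × C(n, k) / C(2n, k).

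For k = 5: 2 × (90/180) × (89/179) × (88/178) × (87/177) × (86/176) = 2 × 0.02952 = 0.059.

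For k = 6, multiply by a further 85/175: 0.05904 × 0.48571 = 0.029.

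| Patients with a liver event | p |
|---|---|
| 1 v 0 | 1.00 |
| 2 v 0 | 0.50 |
| 3 v 0 | 0.25 |
| 4 v 0 | 0.12 |
| 5 v 0 | 0.059 |
| 6 v 0 | 0.029 |

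Under that rule, one to five correctly recorded cases against none would leave both outputs unproduced. Under the loosest rule, any numerical difference, 1 v 0 would trigger them but 1 v 1 would not. Neither result needs any under-reporting.

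**Step 3. What is produced regardless?** PCSA incidence from scheduled and unscheduled, central and local values (SAP 2.4.5.3); the special-interest table that uses laboratory values for ALT elevation (SAP 2.4.5.1); the listing of treatment-emergent serious events (SAP 2.4.5.1); and laboratory listings with out-of-range and PCSA flags (Protocol 11.4.3.2). As described, the laboratory outputs show parameters singly. The SAP text describes no other joint ALT-bilirubin display. Appendix J, which holds the PCSA criteria, was not available for this check.

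**The case against.** The strongest reply is that the underlying information is already planned elsewhere, so the condition affects only convenience of display. Much of that stands, and it rules out three stronger readings.

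- A reader might infer that asymptomatic Hy's law cases are not recorded as adverse events. The protocol says otherwise: the combined elevation is a listed serious event and requires withdrawal from treatment, and either route brings it into the adverse event data without symptoms.
- A reader might infer that a laboratory-only imbalance, say 6 v 1 patients with ALT of 3 to 5 x ULN, would receive no analysis. The ALT PCSA table and worst-value summaries are unconditional. Only the liver-specific outputs would be missing.
- A reader might infer that a case would go unlisted in the study report. A reported case would be in the serious event listing, and its values should be in the flagged laboratory listings that the protocol promises and that SAP 1.6 does not withdraw.

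It is also fair to say that missing a combined case altogether would need a failure at the site, since investigators must review and sign each laboratory report (Protocol 9.2.3.5). How often ALT of 3 to 5 x ULN leads to a consultation or dose interruption, and so becomes an adverse event, depends partly on Appendix F, which was also not available.

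None of this justifies the condition itself. Finding the patient by matching flagged values across listings is not equivalent to a listing made for the purpose, with AST, alkaline phosphatase, conjugated bilirubin, creatine phosphokinase and HCV RNA alongside.

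**Conclusion.** The point holds in a limited form. The two outputs depend on an undefined between-arm imbalance in liver adverse events, which is unsuitable where a single patient matters and which makes a laboratory check rest on site reporting. The consequence is that the only joint ALT-bilirubin displays described in the SAP text may not be produced. It does not follow that cases vanish from the data or the report.

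The five-against-none illustration rests on an assumed p < 0.05 rule and 90 patients per arm. The general conclusion does not need that rule, because equal counts are not an imbalance on any reading. The statement that no other joint display exists is subject to Appendix J. This is a low-cost improvement to a stated rule; no efficacy conclusion depends on it.

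**What to change.** In SAP 2.4.5.3, delete the condition for the Hy's law listing and the peak ALT v peak bilirubin graph. Produce both in every case from all post-baseline central and local values, and print a line saying no cases if nobody qualifies. State in the listing definition whether the ALT and bilirubin elevations must coincide. The time-to-onset and normalization outputs may stay conditional, with imbalance and liver-related events defined.

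The cost is one revised SAP sentence, one extra listing and one extra figure, all from laboratory data already collected. Patient management does not change.
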